#### **2.5.5 Unscheduled visits and local laboratory measurements**

For the by-visit laboratory parameters summary and the PCSA analysis, laboratory measurements performed at both central and local labs will be used.

Unscheduled visit measurements of vital signs and laboratory parameters will be included in the by-visit summaries using specified visit windows.

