- Investigational medicinal product (IMP) to be administered once every two weeks for patients in Dose Regimen 1 and 2 Cohorts and once every week for patients in Dose Regimen 3 Cohort. Patients should be monitored for at least 30 minutes after IMP administration for any signs or symptoms of a hypersensitivity reaction. For patients who complete the extension phase, if the selected dose regimen is dosed once every other week (q2w), then the last IMP injection will occur at Week 154, if the selected dose regimen is dosed once a week (qw), then the last IMP injection will occur at Week 155. Patients will have EOT assessment at the Visit 27 (Week 156). For patients who discontinue the study treatment prematurely during the extension phase, it will be preferable to have EOT assessment 2 weeks after the last IMP injection for Dose Regimen 1 and 2 Cohort patients and 1 week after the last IMP injection for Dose Regimen 3 Cohort patients. In case the patient is unable to meet the planned schedule, the EOT visit

will be used for assessment at the next protocol-defined visit after the last IMP injection. Patients will be asked to return to the site for the EOS assessment 6 weeks after the EOT visit. There will be no IMP injection at the Visit 27 (Week 156).

- f. Height will be measured using stadiometer at sites during the study.
- g. Juvenile Idiopathic Arthritis American College of Rheumatology (JIA ACR) core set includes: global assessment of the severity of disease by the physician, global assessment of overall well-being by the patient or parent, number of joints with active arthritis (defined as swelling within the joint not due to deformity OR limitation of motion and with either pain, tenderness, or both), number of joints with limitation of motion, Childhood Health Assessment Questionnaire (CHAQ), and hs-CRP (2.3.4). If a patient discontinues prematurely before Week 96, hs-CRP must be performed by the central laboratory at EOT.
- h. Juvenile Arthritis Disease Activity Score scoring is explained in [Section 9.4.2](#).
- i. Hematology (blood should be drawn PRIOR TO drug administration): Hemoglobin, hematocrit, red blood cell (RBC) count and morphology (if RBC count is abnormal), white blood cell (WBC) differential (neutrophils, lymphocytes, monocytes, eosinophils, basophils), platelet count, absolute neutrophil count (ANC). If a patient discontinues prematurely before Week 96, the test must be performed by the central laboratory at EOT.

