- g Investigational medicinal product (IMP) to be administered once every other week (q2w). Patients should be monitored for at least 30 minutes after IMP administration for any signs or symptoms of a hypersensitivity reaction. The last IMP injection will occur at Week 94; then patients will have EOT assessment at the Visit 27 (Week 96 for third portion). There will be no IMP injection at the Visit 27.

- h* Height will be measured using stadiometer at sites during the study.
- i* Juvenile Idiopathic Arthritis American College of Rheumatology (JIA ACR) core set includes: global assessment of the severity of disease by the physician, global assessment of overall well-being by the patient or parent, number of joints with active arthritis (defined as swelling within the joint not due to deformity OR limitation of motion and with either pain, tenderness, or both), number of joints with limitation of motion, Childhood Health Assessment Questionnaire (CHAQ), and hs-CRP (2, 3, 4). If a patient discontinues prematurely before Week 48, hs-CRP must be performed by the central laboratory at EOT.
- j* Juvenile Arthritis Disease Activity Score scoring is explained in [Section 9.4.2](#).
- k* Hematology (blood should be drawn PRIOR TO drug administration): Hemoglobin, hematocrit, red blood cell (RBC) count and morphology (if RBC count is abnormal), white blood cell (WBC) differential (neutrophils, lymphocytes, monocytes, eosinophils, basophils), platelet count, absolute neutrophil count (ANC). If a patient discontinues prematurely before Week 48, the test must be performed by the central laboratory at EOT.
- l* Chemistry (blood should be drawn BEFORE drug administration): ALT, AST, ALP, total bilirubin, conjugated bilirubin, unconjugated bilirubin, and albumin will be tested. Complete chemistry (refer to [Section 9.3.4](#)) should be done at Visit 27 EOT (Week 96 for third portion). If a patient discontinues prematurely before Week 48, the test must be performed by the central laboratory at EOT.
- m* Lipids (blood should be drawn BEFORE drug administration): Triglycerides (TG), total cholesterol, high density lipoprotein (HDL) cholesterol, low density lipoprotein (LDL) cholesterol. Patients are required to fast at least 8 hours before the test. At EOT, the test will be performed only for patient who discontinues prematurely before Week 48 and must be performed by the central laboratory.

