9.3.4 Laboratory safety variables

The clinical laboratory data consist of blood analysis (including hematology, clinical chemistry) and urinalysis. Clinical laboratory values will be analyzed after conversion into standard international units. International units will be used in all listings and tables.

Blood will be taken at the study site or at home by qualified personnel. If the blood sample is taken on a day of IMP administration, then blood will be sampled before administration of the IMP. Both central and local laboratories will be used for sample assessments and analysis.

Blood sampling limits, as determined by regulatory guidelines, should be followed with these and any other blood testing during the study. To avoid exceeding blood sample limits, a suggested prioritization of tests is provided to Investigators for reference in the laboratory manual.

The following laboratory tests will be performed at designated visits specified in the study flow charts ([Section 1.2](#))

- Hematology including hemoglobin, hematocrit, red blood cell count and morphology (if red blood cell count is abnormal), white blood cell count (WBC) differential (neutrophils, lymphocytes, monocytes, eosinophils, basophils) including absolute neutrophil count (ANC) and platelet count will be performed at Visit 1 (Day-28 to Day-1, up to 31 days), the Baseline Visit 2 (Week 0, Day 1), Visit 7 (Week 2), Visit 8 (Week 4), Visit 9 (Week 6), Visit 10 (Week 8), Visit 11 (Week 10), and Visit 12 (Week 12) during the initial core treatment phase and at designated visits during the extension phase (see [Section 1.2.2](#))

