- In order to check how the patient's blood cells react on the first dose of study medication, for patients enrolled in the dose-finding and second portions, an additional hematology test must be performed at Visit 6 (Day 12±1 Day) for Dose Regimen 1 and 2 Cohort patients in order to get results before the second dose of sarilumab injection (Visit 7: Week 2, Day 15). For Dose Regimen 3 Cohort patients, an additional hematology test should be performed prior to or at Visit 5 (Day 8) but no earlier than Visit 4 (Day 5) and the results need to be reviewed prior to the second sarilumab injection at Visit 5 (Day 8). The additional hematology test can be done at the central laboratory or at the local laboratory to confirm that the ANC and platelet count are not within the protocol-defined limits for temporary or permanent discontinuation of study drug. For patients enrolled in the third portion without on-site Visit 6, the additional hematology test will be done at the local laboratory before the second dose of sarilumab administration, but no earlier than Day 12. If local laboratory is used, a central laboratory sample for hematology should still be drawn pre-IMP administration at Visit 7 (Day 15, Week 2) as scheduled for Dose Regimen 1 and 2 Cohorts and Visit 5 (Day 8) for Dose Regimen 3 Cohort.
- Complete chemistry profiles will be performed only at the Visit 1 (Day -28 to Day -1, up to 31 days), Baseline Visit 2 (Week 0, Day 1), and Visit 12 (Week 12) during the initial core treatment phase and at designated visits during the extension phase (see [Section 1.2.2](#)).
 - Complete chemistry includes: Sodium, potassium, chloride, bicarbonate, blood urea nitrogen (BUN), creatinine and creatinine clearance, glomerular filtration rate (using the modified Schwartz formula), calcium, phosphate, total protein, albumin, ALT, AST, alkaline phosphatase (ALP), total bilirubin, conjugated bilirubin, and unconjugated bilirubin

- At Visit 7 (Week 2), Visit 8 (Week 4), Visit 9 (Week 6), Visit 10 (Week 8), and Visit 11 (Week 10) during the initial core treatment phase and at designated visits during the extension phase (see [Section 1.2.2](#)) only an abbreviated chemistry profile (ALT, AST, ALP, total bilirubin, conjugated bilirubin, unconjugated bilirubin, and albumin) will be measured.

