#### **2.4.5.3 Analyses of laboratory variables**

The summary statistics (including number, mean, median, SD, minimum and maximum) of all laboratory variables (laboratory values and changes from baseline) will be calculated for each visit or study assessment (baseline, each post-baseline time point, endpoint) by dose regimen cohort. This section will be organized by biological function as specified in [Section 2.1.4.4](#).

In addition, for all laboratory parameters, the mean value and mean change from baseline at each scheduled visit will be plotted by dose regimen cohort.

The incidence of PCSAs ([Appendix A](#)) at any time during the TEAE period will be summarized by biological function and dose regimen cohort whatever the baseline level and/or according to the following baseline status categories:

- Normal/missing
- Abnormal according to PCSA criterion or criteria.

For lipids, the NCEP APTIII classification will be used for the baseline.

The incidence of PCSAs at any time during the post-study period will be summarized by the actual dose regimen cohort received in the 12-week core treatment period.

The incidence of abnormal laboratory values at any time during the TEAE period will be summarized in shift tables by biological function and dose regimen cohort whatever the baseline level and/or according to the following baseline status categories:

- Normal/Missing
- Abnormal high according to the normal range
- Abnormal low according to the normal range

Listings will be provided with flags indicating the out of range values as well as the PCSA values.

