#### **2.5.4 Windows for time points**

For efficacy parameters, discontinuation visit will be mapped to the scheduled visit for the analyses. If a discontinuation visit happens at a regular visit, then the visit number will be reassigned as the regular visit number where an assessment is planned. If a discontinuation visit happens between 2 regular visits, then the visit number will be reassigned to the next visit number where an assessment is planned. For example, if a discontinuation visit happens between Visits 5 and 6, then the visit number will be reassigned as 6.

Visit windows based on days relative to the first IMP dose will be used to map the laboratory values, vital signs, ADA, and PK measurements to each scheduled visit (see [Appendix B](#) for details). The following rule will be applied when mapping the measurements to the visit:

1. When a patient has more than one measurement on the same lab parameter (or vital sign) on the same date, then the one with the later/largest sample ID will be used.
2. For the same laboratory parameter (vital sign), if a patient has more than one measurement at different dates within the same visit window, the scheduled measurement that is closest to the target date will be used. If there is no scheduled measurement within the visit window, the unscheduled measurement that is closest to the target date will be used.
3. When a patient has more than one measurement on the same lab parameter with the same distance from the target date, the one with the latest date will be used.

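### By-visit laboratory means and changes from baseline pool central and local results, and no rule separates them by laboratory or prefers the central value

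*SAP*

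**What the plan says.** Protocol 9.3.4 sets up two sources: "Both central and local laboratories will be used for sample assessments and analysis". SAP 2.4.5.3 describes summary statistics "of all laboratory variables (laboratory values and changes from baseline) will be calculated for each visit or study assessment", by dose regimen cohort, and adds plots of the mean and the mean change at each scheduled visit. SAP 2.5.5 feeds both sources into that summary and into the PCSA analysis: "For the by-visit laboratory parameters summary and the PCSA analysis, laboratory measurements performed at both central and local labs will be used".

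SAP 2.5.4 chooses among competing results in three steps. If there are several "on the same date, then the one with the later/largest sample ID will be used". If the dates differ within a window, the scheduled result nearest the target day is taken. Ties go to the latest date. Laboratory is not a criterion at any step.

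On where samples go, Protocol 9.3.4 is explicit for one test. In the third portion, "the additional hematology test will be done at the local laboratory before the second dose of sarilumab administration, but no earlier than Day 12". In the dose-finding and second portions the same test may be central or local, and a central hematology sample is still drawn when the local laboratory is used. For end of treatment, the hematology and chemistry footnotes in Protocol 1.2.2.1 and 1.2.2.2 say: "If a patient discontinues prematurely before Week 96, the test must be performed by the central laboratory at EOT". Those in 1.2.2.3, for the third portion, say: "If a patient discontinues prematurely before Week 48, the test must be performed by the central laboratory at EOT". The hs-CRP footnotes use the same two cut-offs.

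**The concern.** A PCSA count asks whether any result crossed a limit, so every available result belongs in it. A mean change from baseline asks how far a quantity moved, and it assumes the same measuring system at both ends. If the share of local results differs by portion or rises with time, part of any movement in the mean may come from the change of laboratory.

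The study is open-label with no control arm, so change from baseline is the main quantitative laboratory signal and no concurrent group would show the same artefact. Long-term safety is a secondary objective, and the protocol summary names a plot of mean neutrophil count over time as an output. The visible SAP text has no central-only summary, no analysis by laboratory and no rescaling of the means to reference ranges. SAP 2.1.4.4 converts units only.

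**Working it through.** The plan gives no figure on this point to reproduce. The check has three steps.

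**1. Where two results can compete**

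- For Dose Regimen 3, the extra hematology test may be done at or before Visit 5 (Day 8). If it is local, Protocol 9.3.4 and 10.1.3 still call for a central sample before dosing, preferably at Visit 5. A central and a local result on one date are therefore foreseen, and the sample-ID rule decides between them. Sample IDs from two laboratories carry no information about which result to prefer.
- For the q2w regimens, Protocol 10.1.2 tells third-portion patients to have the local test before Visit 7, so the dates should differ and the nearest-to-target rule applies.

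**2. Possible share of local values in the extension**

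This step is conditional on reading the end-of-treatment footnotes to mean that testing is local after Week 48 in the third portion and after Week 96 in the first two. It also assumes full retention.

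Inputs:
- Third portion: 28 patients (Protocol 6.1).
- Selected regimen before the third portion: 18 evaluable in each of two weight groups, 2 × 18 = 36 (Protocol 6.1).
- Planned inflation: up to 72 enrolled for about 60 evaluable (protocol summary), so 36 × 72/60 = 43.2.
- All treated: about 100 (Protocol 6.1).

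Share local at Weeks 60-96:
- Selected regimen, evaluable count: 28/(36 + 28) = 28/64 = 43.8%.
- Selected regimen, inflated count: 28/(43.2 + 28) = 28/71.2 = 39.3%.
- Any-dose group: 28/100 = 28%.

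After Week 96 only patients from the first two portions remain on schedule, and on this reading all their values would be local. The baseline would be mainly central: screening eligibility results come from the central laboratory (Protocol 7.2.2, E 24), and central sampling is the default during the core phase.

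**3. What that would do to a mean**

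Shift in the mean = (share local) × d, where d is the relative difference between laboratories. The documents give no value for d, so the values below are assumptions that show the range.

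| d (assumed) | Any-dose, Weeks 60-96 (28%) | Selected, Weeks 60-96 (39.3-43.8%) | After Week 96 (100%) |
|---|---|---|---|
| 5% | 1.4% | 2.0-2.2% | 5% |
| 10% | 2.8% | 3.9-4.4% | 10% |
| 20% | 5.6% | 7.9-8.8% | 20% |

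The pattern would be a partial step after Week 48 and a full one after Week 96, with no change in any patient.

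**The case against.** Much of the opposing case stands.

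- **The late switch is not stated.** The footnotes speak only of patients who stop early. They do not say where later samples go, and no visible text says that ALT, AST or hs-CRP is ever measured locally. A reader might infer that the plan moves to local laboratories at Weeks 48 and 96. That is plausible, but it is an inference, and everything in steps 2 and 3 depends on it.
- **Early rows are largely protected.** Central samples are still drawn in the core phase and scheduled values take priority. A step first seen at Week 60 or 108 would not resemble drug onset, so it is too strong to say that the artefact could not be told from a drug effect.
- **A Day 15 clash in the third portion.** A reader might infer that the local test and the central Visit 7 sample share a date. Protocol 10.1.2 places the local test before Visit 7. With Visit 7 on Days 14-16 and the local test on an earlier day from Day 12, the central value is nearer Day 15 or wins the tie as the later date, except when the local test is on Day 15 and Visit 7 on Day 16.
- **Consequences for ACR response or PD.** A reader might extend the point to these through hs-CRP. SAP 2.5.5 governs the laboratory summary and PCSA only. The PD endpoint is at Week 12 or EOT (SAP 2.1.8), and an ESR version of ACR30 is already planned (SAP 2.4.6.2).
- **Categorical outputs partly adjust already.** Liver-enzyme PCSAs are multiples of ULN, shift tables use normal ranges, and the Grade 3-4 neutropenia listing includes central and local retests.
- **Some text cannot be seen.** The hematology, chemistry and hs-CRP columns of SAP Appendix B Table 2, and SAP 1.5, 1.6 and 2.4.5.6, are not visible. A safeguard there cannot be ruled out.
- **Restricting the tables to central values would cost late safety data.** This is right, and it is why the fix adds a central-only version and leaves the pooled one in place.

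None of this supports an unlabelled mixture in a mean change, or a sample-ID rule as the choice between two laboratories.

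**Conclusion.** The point holds as a minor one. Two parts are certain from the text: the by-visit means and changes pool both sources, and no visible rule prefers or separates them. Source differs by portion for one test, the hematology sample before the second dose.

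The larger consequence is conditional. If extension testing becomes local as the footnotes suggest, about 39-44% of selected-regimen values at Weeks 60-96 (about 28% in the any-dose group) and all values after Week 96 would be local, at full retention and against a mainly central baseline. The share would move with unequal retention; the ACR30 requirement for entering the extension applies only to the first two portions and would tend to raise it. The between-laboratory difference is unknown, so no size of bias can be claimed. The risk is that such a difference is read as late drift on treatment. The analysis is descriptive, so no test result is at stake.

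**What to change.** In SAP 2.5.4 and 2.5.5:

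1. When a central and a local value fall on the same date or in the same visit window, use the central value in by-visit summaries. This replaces the sample-ID choice in the foreseen Dose Regimen 3 case at Day 8.
2. Add a central-only version of the by-visit means, changes from baseline and mean plots. In the pooled version, flag laboratory source so that rows that are wholly or partly local are labelled and not read as a drug effect.
3. Keep local values in PCSA counts, cytopenia grades and listings, using the reporting laboratory's range where the criterion depends on one.

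The cost is some SAP wording, a source flag in the programs and a second set of by-visit tables, whose late rows may hold few or no patients. No late safety data are lost. If extension samples prove to be central throughout, the two versions will nearly agree and little changes.

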#### **2.5.6 Pooling of centers for statistical analyses**

Pooling by region may be performed, but to be determined.

#### **2.5.7 Statistical technical issues**

None.

### 3 INTERIM ANALYSIS

A DMC, composed of independent pediatric rheumatologists who are not participants in the sarilumab pediatric clinical studies, are not sponsor representatives, and do not have any conflict of interest with regard to study outcomes, will monitor patient safety by conducting formal reviews of accumulated safety data and will recommend the appropriate course of action for the study to a DEC, composed of sponsor representatives. The DMC members' responsibilities and the process for data review are described in the DMC Charter.

The DEC will review the study data on a continuous basis as well as between dose regimen cohorts. The DEC will decide the appropriate course of action for the study, such as continuation to the next dose regimen cohort or modifications to the protocol, subject to the DMC recommendations regarding safety. The DEC members' responsibilities and the process for data review are described in the DEC Charter.

[REDACTED]

[REDACTED]

[REDACTED]

[REDACTED]

[REDACTED]

In addition to this ongoing review of data for dose escalation and futility, [REDACTED] [REDACTED] three formal interim analyses for pcJIA will be performed prior to the conclusion of the extension part for all patients:

- The first formal interim analysis will be performed once sufficient Week 12 data have been observed from the dose-finding portion to allow a selection of a dose regimen for more detailed investigation.
- Second interim analysis will be performed approximately one year from the time every patient enrolled in the dose-finding and second portions has started receiving the selected dose regimen (either new enrolled patients or patients already in the extension phase). Only patients enrolled in the dose-finding and second portions will be included in this interim analysis.
- Third interim analysis (pcJIA only) will be performed approximately 1 year from the time the last patient enrolled in the third portion.

The primary objective is PK estimation, and there is no formal hypothesis testing, thus there are no statistical implications for the summary and reporting of the final data at the conclusion of the extension.

## **4 DATABASE LOCK**

The first database lock will occur approximately 4 weeks after sufficient Week 12 data have been observed from the dose-finding portion.

The second database lock will occur approximately 4 weeks after one year from the time every patient enrolled in the first and second portions has received the selected dose regimen (either new enrolled patients or patients already in the extension phase).

The third database lock (pcJIA only) will occur approximately 4 weeks after one year from the time the last patient enrolled in the third portion.

The final database lock, including the extension, will occur approximately 4 weeks after the last patient has completed the end of study visit.

